Aim 1. Characterize the acute analgesic effects of alcohol in individuals with chronic temporomandibular joint and muscle disorder (TMD). Despite evidence that self-medication of pain with alcohol is common among people with TMD (Riley and King, 2009), quantitative data regarding the magnitude of this effect is largely lacking. Similarly, it is unclear whether the acute analgesic effects of alcohol may differ between individuals with and without chronic pain. We believe TMD is an ideal model with which to test the acute effects of alcohol intake on clinical pain because it is a relatively common condition (~5-12% of the general population; Goulet et al., 1995; Johansson et al., 2006), and clinically relevant pain can be reliably evoked in laboratory settings by applying pressure at the insertion of the masseter muscle (i.e., pressure algometry; Brown et al., 2000). **Hypothesis (H)1.** We hypothesize that consumption of a dose of alcohol sufficient to produce a breath alcohol concentration (BrAC) of ~ .08 g/dL will be associated with significant reduction in pain sensitivity compared to placebo in both TMD patients and healthy controls, and **H2.** acute alcohol will be associated with greater ratings of perceived relief than placebo following pain induction. Evidence from the animal literature suggests chronic pain may modulate the acute effects of opioid administration. Furthermore, chronic pain is associated with maladaptive plasticity in brain regions that underpin acute alcohol effects, including medial prefrontal cortex and nucleus accumbens (for review, see Egli et al., 2012). Thus, although it is likely that TMD patients may experience differential effects of alcohol use on pain sensation compared to healthy controls, the directionality of this effect is currently unclear. Thus, we predict **H3.** chronic pain status will moderate the magnitude of alcohol analgesia but ask as an empirical question **(E)1.** whether the effect of alcohol on pain sensitivity will be stronger or weaker in this group. Attenuated analgesic response in TMD patients would be consistent with rat studies suggesting neuropathic pain shifts opioid dose-response curves, increasing opioid self-administration (Egli et al., 2012). In contrast, an

exaggerated analgesic response would suggest alcohol use might be especially negatively reinforcing.

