Aim 2. Determine the influence of typical alcohol use and expectation of pain relief with alcohol use on magnitude of alcohol analgesia and associated feelings of relief. Studies of alcohol analgesia in healthy adults have indicated that individual patterns of typical alcohol use, motivation to drink, and personality factors may modulate alcohol analgesia, suggesting a critical role of conditioning and expectancies (Brown and Cutter, 1977; Cutter et al., 1979; Ralevski et al., 2010). However, this question has never been directly examined, either in healthy adults or those with chronic pain. **H4.** We predict individuals with stronger positive expectancies regarding alcohol analgesia will have significantly stronger analgesic responses to alcohol administration. **H5.** Based on previous research, we predict that individuals who endorse greater and more frequent alcohol consumption will experience a greater analgesic effect of alcohol, independent of the effect of expectancies. Finally, we ask as **E2.** whether chronic pain status will be associated with stronger expectancies of pain relief following alcohol consumption and **E3.** greater ratings of pain relief during pressure algometry after drinking.

6. Research Plan:

General Approach. For this study of current non-problem drinkers, we propose a repeated-measures, double blind placebo-controlled factorial design with chronic pain status (TMD vs. healthy control) as a between-subjects factor and alcohol administration (Alcohol Dose: placebo, 0.08 g/dL) as a within-subjects factor. The study will include both men and women. Study procedures will occur at the Center for Pain Research and Behavioral Health of the University of Florida under supervision of the PI (JB).

Methods

Participants. Individuals seeking care for temporomandibular joint and muscle disorder (TMD) (n=25) will be recruited for the study via flyers, word of mouth, internet/local radio advertisements, and [name] orthodontic clinic. A sample of healthy social drinkers without TMD (HC) will also be recruited as a comparison group (n=25). Individuals aged 21-45 years will be recruited to avoid any vulnerability to acute neurobehavioral effects of alcohol associated with older age (e.g., [name] et al., 2016a). Because TMD is more prevalent in women than men (~2:1; Campbell et al., 2017), we anticipate the final sample will consist of approximately 2/3 women.

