
Data Analysis Strategy. Data will be analyzed using SPSS 24 (IBM Corp., Armonk, NY).

Aim 1. Determine the effect of chronic pain status on magnitude of alcohol analgesia and associated feelings of relief. To assess hypotheses and empirical questions related to Aim 1, chronic pain status will be included as an independent variable in repeated measures general linear models analyses (rmGLM; SPSS GLM procedure; repeated: dose), with QST measures, associated relief ratings, and SEAS measures as dependent variables. Demographic, personality/affective (i.e., BDI/STAI/IRQ/BFI), substance use-related (recent alcohol use/alcohol use disorder symptomatology), pain-related (TMD severity), and biological (i.e., approximated menstrual phase for female participants) variables will be included as covariates should any correlate significantly with magnitude of alcohol analgesia or relief ratings.

Aim 2. Determine the influence of typical alcohol use, and alcohol analgesia-related expectancies on magnitude of alcohol analgesia and associated feelings of relief. A combination of approaches will be used to address Aim 2. Simultaneous multiple regression of alcohol analgesia expectancy and typical alcohol consumption

(estimated in ounces of absolute ethanol consumed per day derived from the AUQ) on QST measures will be used to evaluate H4 and H5. As in Aim 1, rmGLM will be used to assess E2 and E3.

Power Analysis. Power analyses for the proposed work are based on effect sizes derived from our initial feasibility study (see attached grant application for details) and were performed assuming two-tailed hypothesis tests with alpha=.05. Effect sizes are reported as Cohen's d, Pearson's r, or R2 (Cohen, 1988). Analyses indicated N=50 would provide excellent (98%) power to detect analgesic effects of alcohol administration on QST measures (Cohen's d > .58) and correlations between VAS ratings of relief and alcohol analgesia (r = .64). Critically, this sample size will also provide 80% power to detect small-to-medium sized effects (d > .40; r > .37; R² > .14) for which prior estimates are not available (e.g., the effect of chronic pain status on alcohol analgesia and subject alcohol affects). *We will recruit a total of 60 qualified subjects over the course of the project to account for 10% anticipated participant dropout before completing all study visits.*

7. Possible Discomforts and Risks:

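### H1 claims analgesia in both groups, but the planned model tests, and the 98% power describes, only the dose effect pooled over all 50 participants

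*Combined protocol and SAP*

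**What the plan says.** Under Specific Aims, Aim 1, H1 predicts a "significant reduction in pain sensitivity compared to placebo in both TMD patients and healthy controls". H3, in the same aim, predicts that "chronic pain status will moderate the magnitude of alcohol analgesia", and E1 leaves open whether the effect is stronger or weaker in TMD patients.

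The Research Plan sets 25 TMD patients against 25 healthy controls, with "alcohol administration (Alcohol Dose: placebo, 0.08 g/dL) as a within-subjects factor". Each participant therefore supplies an alcohol-placebo difference.

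For Aim 1, the Data Analysis Strategy says that "chronic pain status will be included as an independent variable in repeated measures general linear models analyses", with dose repeated and the QST measures, relief ratings and SEAS measures as outcomes. It specifies no dose contrast within a group and no criterion for declaring H1 met in both.

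The Power Analysis, "assuming two-tailed hypothesis tests with alpha=.05", reports that "N=50 would provide excellent (98%) power to detect analgesic effects of alcohol administration on QST measures" at d above .58. It gives no power within a group of 25 and none for success in both groups. It plans to recruit 60 participants to allow for 10% dropout.

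**The concern.** Three parts of the plan address different questions. H1 is a statement about each of two groups. The model, as described, delivers a dose main effect averaged over the groups and a dose-by-group interaction. The only power figure for analgesia belongs to the averaged effect.

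A significant average does not show an effect in each group. If controls respond and TMD patients do not, the dose main effect can still reach significance, and nothing in the plan would stop H1 being reported as supported for TMD patients, the population Aim 1 is about. The plan itself treats unequal effects as likely: H3 predicts them, and E1 allows for a weaker response in TMD. A reader of the Power Analysis could also take 98% as the chance of confirming H1 as worded.

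**Working it through.** **Inputs.** Two-sided alpha .05, N = 50 and d = .58 (Power Analysis); 25 per group and dose within subject (Research Plan). The type of d is not stated. I take it as the standardised paired difference, because that reading reproduces the plan's figure.

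**Formula.** Power of a two-sided paired t-test from the noncentral t distribution, with noncentrality d × √n and n − 1 degrees of freedom.

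**1. The plan's own figure.** n = 50: noncentrality .58 × √50 = 4.10, critical t 2.01, power 98.0%. The result is the same to one decimal with 48 df, as in the rmGLM. The 98% is reproduced as a pooled paired test on all 50. A two-sample comparison of 25 with 25 would give only 52%, so it is not the source of the figure.

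**2. One group.** n = 25: noncentrality .58 × 5 = 2.90, critical t 2.06, power 79.5%.

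**3. Both groups.** The groups are independent, so at equal effects .7946 × .7946 = 63.1%. A simulation gave 79.7% per group and 63.4% for both.

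**4. Variations that favour the plan.**

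| Setting (d = .58 in each group) | Per group | Both |
|---|---|---|
| 25 per group, separate error terms | 79.5% | 63% |
| 25 per group, rmGLM pooled error (48 df) | 81% | 66% |
| 27 per group (60 × 0.9 = 54 completers, split equally) | 83% | 68% |

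The smallest size giving 80% for both is 33 completers per group. With 25 per group, 80% for both needs d of about .67.

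**5. Unequal effects averaging .58 (illustrative splits, 25 per group).**
- .48 and .68: 63.4% × 90.3% = 57% for both.
- .38 and .78: 44.6% × 96.2% = 43% for both.

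**6. Only one group responds (d = .58 and 0, equal SDs).**
- Pooled dose effect: the average is .58 / 2 = .29; noncentrality .29 × √50 = 2.05, 48 df, power 52%.
- Dose-by-group interaction: the difference is .58; noncentrality .58 × √(25/2) = 2.05, 48 df, power 52%.

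The two noncentralities are identical, so in this case the interaction is no more likely to expose the missing response than the main effect is to be significant.

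**7. Sensitivity to the type of d.** If .58 were scaled to the raw SD, the paired d would be .58 / √(2(1 − ρ)), where ρ is the correlation between sessions, which the plan does not give.

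| Assumed ρ | Paired d | Pooled, n = 50 | Per group, n = 25 | Both |
|---|---|---|---|---|
| 0.3 | .49 | 92% | 65% | 43% |
| 0.5 | .58 | 98% | 79.5% | 63% |
| 0.7 | .75 | 99.9% | 95% | 90% |

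The stated 98% fits the paired d, or ρ = 0.5. It does not fit the other two rows.

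**The case against.** A reader might infer that the 98% is miscalculated, or that the design lacks the power it quotes. The documents do not support that. The sentence ties the figure to N = 50 and to the effect of alcohol administration on QST measures, does not mention H1, and is right for that effect.

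The strongest defence is that H1 can be read as a dose effect across a sample containing both groups, with group differences left to H3. On that reading the rmGLM is a standard and sufficient analysis, and 98% applies. This is a possible intention, but the wording of H1 would then need to change, because a significant reduction in both groups says more than a significant average. The interaction test under H3 helps only in part, as step 6 shows.

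It is also fair to say that 79.5% and 63% are conditional. They assume a paired d, equal effects, one QST measure although several are planned, and exactly 25 per group. The plan writes d above .58; at d = .65 the figures would be 88% per group and 77% for both. Per-group power at .58 is in effect the conventional 80%. Finally, the Abstract says that the study is partly meant to supply feasibility and effect-size data. These points argue for stating assumptions and a range, and against calling the trial underpowered. They do not supply the missing contrast or decision rule.

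**Conclusion.** The concern holds as a mismatch between hypothesis, analysis and power statement; it is not an arithmetic error. The 98% stands for the pooled dose effect. For H1 as worded, the plan has no matching test and no matching power.

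At a paired d of .58 in each group, two-sided alpha .05 and one QST measure, power is about 80% per group (79.5% to 83%) and about 63-68% for both. It falls to 57% or 43% for both under the illustrative unequal splits. If only one group responds at .58, the pooled effect is still significant about 52% of the time.

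The power figures depend on d being the standardised paired difference, which is inferred from the match to 98% and not stated. The gap between H1 and the planned test does not depend on that assumption.

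**What to change.** Choose one of two remedies before analysis; both are valid.

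- **Keep the two-group claim.** Pre-specify the alcohol-placebo contrast within each group, as simple effects of dose in the rmGLM, and claim H1 in both groups only if both are significant. Because both must succeed, no alpha adjustment between the groups is needed. Add to the Power Analysis that, at a paired d of .58 in each group and for one QST measure, power is about 80% per group and 63-68% for both, and lower for both if the effects differ around that mean as H3 predicts.
- **Reword H1 as the pooled dose effect.** Keep the planned main-effect test and report the alcohol-placebo estimate within each group with a confidence interval, without claiming an effect in each group from the pooled test.

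Under either remedy, label 98% as power for the pooled dose effect only, and state that d is the standardised paired difference, or give its actual definition.

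The cost is a few sentences and two contrasts on data already planned, with no added visits. The downside of the first remedy is a less favourable power figure for the two-group claim: 80% power for both at d = .58 would take 33 completers per group, 66 in all, against the 54 expected from recruiting 60. The second gives up the formal claim in each group.

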Official Title: Acute Effects of Alcohol Use on Chronic Orofacial Pain

NCT: 04019093

Version Date: 7/2/2021

Protocol

1. Project Title:

Acute Effects of Alcohol Use on Chronic Orofacial Pain

2. Investigator(s):

[name] (PI)
[name] (Co-I)
[name], PhD (Co-I)

3. Abstract:

It has long been suggested that alcohol has analgesic properties. Data suggest that about 25% of chronic orofacial pain patients endorse the use of alcohol for pain management. However, the biopsychosocial mechanisms underlying this intuitive interaction are not well established. Studies of healthy individuals using quantitative sensory testing (QST) have shown that familial risk for alcoholism, as well as psychological characteristics like mood and personality, may act as critical factors modulating individuals' sensitivity to alcohol analgesia. However, to our knowledge, the acute pain-relieving effect of alcohol intake in individuals with chronic pain has never been systematically studied. This relationship is important to understand because alcohol analgesia may be associated with relief. Relief from pain may act as a potent negative reinforcer for alcohol intake, which, in turn, can have adverse health effects by increasing risk of developing an alcohol use disorder in people with chronic pain. Self-medication of pain with alcohol may also result in harmful drug interactions, risk of injury due to neurobehavioral impairment, and even development of painful alcohol neuropathy. The overall goal of this proposal is to test the analgesic effects of acute alcohol consumption in individuals with chronic pain and a comparison group of pain-free controls, and identify critical biopsychosocial modulators of alcohol analgesia. These efforts will inform research and clinical/translational efforts regarding modifiable and unmodifiable factors related to risk associated with self-medication of chronic pain using alcohol, and provide critical feasibility and effect size data for future proposals.

4. Background:

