Selection Criteria. TMD diagnosis will be confirmed by [name], a practicing orthodontist and orofacial pain expert, or a qualified dentist designated by [name] in situations where he may not be available, based on published Research Diagnostic Criteria (Schiffman et al., 2014). As guided by the Research Diagnostic Criteria for TMD, TMD participants in the TMD group must report TMD-related orofacial pain over the 6 months preceding screening. Participants will be excluded if they have a history of a chronic pain condition other than TMD (e.g., osteo- or rheumatoid arthritis, fibromyalgia, complex regional pain syndrome); report use of opioid analgesics; current

major depression; history of any psychotic disorder; undercontrolled hypertension or diabetes

(as reflected by self-report); neurological disease (e.g., multiple sclerosis, epilepsy, amyotrophic lateral sclerosis, Parkinson's disease); serious medical illness (e.g., hepatitis, HIV/AIDS); impaired cognitive function; or history of drug or alcohol dependence. Because chronic smoking is associated with adverse neurobehavioral changes ([name] et al., 2011; Durazzo et al., 2013), participants must be non-smokers. Participants must also be current drinkers (i.e., consume at least 1 drink/month over the last 6 months). Alcohol abstinent or naïve individuals will be excluded. To avoid confounding effects of binge-drinking patterns, participants must score lower than an 8 on the AUDIT. To increase ecological validity and ensure feasibility of recruitment, use of prescription medications will be allowed provided they do not contraindicate alcohol use ([name] et al., 2014; Gilbertson et al., 2009).

Screening Measure	Domain	Exclusionary Cutoff
BDI-II	Depressive Symptomology	≥ 20 (moderate depression)
STAI	State/Trait Anxiety	Not Exclusionary
AEQ	Alcohol Expectancies	Not Exclusionary
AUQ	Alcohol Use Pattern	Not Exclusionary
AUDIT	Alcohol Use Disorder Sx	≥ 8
PILL	Somatic preoccupation /neuroticism	Not Exclusionary
FTQ	FH Assessment	Not Exclusionary
PSQI	Sleep Quality	Not Exclusionary
BRS	Resilience to stressors	Not Exclusionary
DIS	Ability to tolerate physical discomfort	Not Exclusionary
EAA	Expectancies regarding pain relief from alcohol	Not Exclusionary
PCS	Pain catastrophizing	Not Exclusionary
PASS-20	Pain-related Anxiety	Not Exclusionary
IRI	Empathy	Not Exclusionary
OHIP-TMD	TMD Pain Severity and Interference	Not Exclusionary

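### The 80% power at d > .40 holds for the pooled within-subject alcohol effect; the 25 vs 25 TMD-control contrast named as its example has about 28% power there and needs d of about 0.8

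*Combined protocol and SAP*

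**What the plan says.** Section 6, Power Analysis, assumes two-sided tests at alpha .05. It first claims 98% power at N=50 for the analgesic effect of alcohol at d > .58. It then says "this sample size will also provide 80% power to detect small-to-medium sized effects (d > .40", adding r > .37 and R² > .14, for effects without prior estimates. The example given is "e.g., the effect of chronic pain status on alcohol analgesia and subject alcohol affects". The paragraph does not say which threshold belongs to which test, which SD standardises d, or what correlation between sessions was assumed.

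Section 6, General Approach, describes "a repeated-measures, double blind placebo-controlled factorial design with chronic pain status (TMD vs. healthy control) as a between-subjects factor", with alcohol dose as the within-subjects factor. Under Participants, 25 people with TMD are to be recruited, and "A sample of healthy social drinkers without TMD (HC) will also be recruited as a comparison group (n=25").

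The group contrast carries stated questions. H3 in section 5 predicts that "chronic pain status will moderate the magnitude of alcohol analgesia but ask as an empirical question" (E1) which direction the difference takes. E2 asks "whether chronic pain status will be associated with stronger expectancies of pain relief following alcohol consumption". Under Data Analysis Strategy, Aim 1 is headed as the question of pain status and is tested in a repeated-measures GLM with group as the independent variable.

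**The concern.** A reader will take the sentence to mean that 50 participants can detect a small-to-medium difference in alcohol analgesia between TMD patients and controls. But a between-subjects contrast uses 25 against 25, whereas the dose effect uses all 50 as their own controls. At the same standardised effect the two cannot have the same power.

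If the sentence is wrong for the group contrast, a null on H3 could be taken as evidence against a moderate moderation that the study was unlikely to detect. The plan has no rule for reading such a null. The Abstract also says the study is meant to "provide critical feasibility and effect size data for future proposals", so the next study's planners will rely on the stated sensitivity.

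**Working it through.** **Inputs.** Two-sided alpha .05; N = 50; d = .58 at 98% and d = .40 at 80%; r > .37; R² > .14 (all Power Analysis). 25 per group (Participants). Two dose levels within subject (General Approach). The between-session correlation ρ is not given, so a range is assumed. Power is from the noncentral t or F distribution.

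**1. Reproduce the stated figures.** Paired test on all 50, noncentrality d·√50:

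- d = .58: .58 × 7.071 = 4.10, power 98.0% (stated 98%).
- d = .40: .40 × 7.071 = 2.83, power 79.2% (stated 80%). Exactly 80% is reached at d = 0.404.

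Both printed d figures fit one method: the pooled within-subject effect.

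**2. The group contrast.** With two dose levels, the group-by-dose term equals a two-sample t-test on alcohol-minus-placebo change. Noncentrality is d/√(1/25 + 1/25) = d/0.283, with 48 df:

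- d = .40: .40/0.283 = 1.41, power 28.3%.
- 80% power needs d = 0.81.
- Keeping d = .40 at 80% needs 100 per group (80.4%).
- With 60 recruited and 10% lost, 60 × 0.9 = 54, or 27 per group: 30.2% at d = .40, and 80% at d = 0.78.

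**3. Compare the three printed thresholds.** For two equal groups r = d/√(d² + 4), so d = 2r/√(1 − r²):

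| Printed threshold | Equivalent for two equal groups | Power at 25 vs 25 |
|---|---|---|
| d = .40 | r = .20, R² = .04 | 28.3% |
| r = .37 | d = 0.80 | 78.8% |
| R² = .14 | d = 0.81 | 79.8% |

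The r and R² entries are about right for this contrast; the d entry is not.

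**4. If d is in single-session SDs.** The change-score SD is then √(2(1 − ρ)) single-session SDs. The effect in change-score units is .40/√(2(1 − ρ)), and the detectable difference is 0.809·√(2(1 − ρ)):

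| Assumed ρ | Power at 0.40 | Difference for 80% power |
|---|---|---|
| .3 | 22% | 0.96 |
| .5 | 28% | 0.81 |
| .7 | 43% | 0.63 |
| .8 | 59% | 0.51 |

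Power reaches 80% at 0.40 only when ρ = 1 − (.40/0.809)²/2 = .88. At that ρ, the paired test at .58 would have essentially 100% power and at .40 over 99.9%, which does not fit the stated 98% and 80%.

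**5. E2.** The expectancy score ("Expectancies regarding pain relief from alcohol") is listed among the screening measures in Table 1. E2 is therefore a plain 25 vs 25 comparison with no session correlation: 28% at d = .40, and 80% at d = 0.81.

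**6. Precision.** The 95% CI half-width for the group difference is 2.011 × √(2/25) = 0.57 SD.

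**The case against.** The strongest reply is that the figure may have been computed for the right test. A mixed-ANOVA interaction with f = .20 and ρ = .5 has noncentrality .04 × 50 × 2/.5 = 8 and power 79.1%. Under the usual d = 2f conversion, f = .20 prints as d = .40. The documents cannot exclude this route. But in a 2×2 interaction, f = .20 means a difference between groups in the alcohol effect of 4 × .20 = 0.80 SD. Printing it as d = .40 halves the effect required, so the reader is misled either way.

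The paragraph also refers to an attached grant application for details, and the SD behind d may be defined there. That is fair, and it means the origin of the error cannot be settled. It does not change what this document tells its reader.

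Three further points stand in part:

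- The group effect is only an example beside three thresholds, two of which are about right. That narrows the fault to the d entry and the label.
- E2 is not named in the sentence. It belongs here only as one of the contrasts for which no separate power figure is given.
- The plan does not say that a null would be read as no moderation, and it states no expected size for it. The chance of missing an effect of .40 illustrates the gap and does not forecast the result.

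Covariates will not close the gap unless they explain about 76% of change-score variance, from 1 − (.40/0.809)². The plan assumes no such figure.

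**Conclusion.** The concern holds. As printed, d > .40 at 80% power is wrong for the contrast given as its example. In change-score SDs, the scale on which the stated 98% and 80% both reproduce, power for 25 vs 25 is 28% and the detectable effect is 0.81. A true moderation of d = .40 would be missed about 72% of the time. On a single-session scale the miss rate is about 41% to 78% for assumed correlations of .8 down to .3. No reading consistent with the paragraph's other figures restores 80% at a group difference of .40.

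The 98% claim for the alcohol effect is sound, and neither the sample size nor the planned model is in question. This should be corrected because H3 is a stated prediction and its sensitivity is misdescribed.

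**What to change.** Rewrite the sentence so that each threshold is tied to its contrast:

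1. Pooled within-subject alcohol effect, N = 50: 80% power at d of about .40.
2. TMD vs control contrasts (H3/E1, E2, E3 and subjective alcohol effects), 25 per group: 80% power at d of about 0.8, equivalent to the r > .37 and R² > .14 already printed.
3. Define the SD used for d in each case, and give any between-session correlation assumed.
4. Drop the small-to-medium label for the group contrasts.

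It would also help to say that group contrasts will be reported as estimates with 95% CIs (about ±0.57 SD) and that a non-significant result will not be read as absence of moderation. Separately, and of less weight, Participants gives 25 + 25 while Power Analysis recruits 60 with 10% dropout, leaving 54. The difference is on the safe side, but one set of figures should be used.

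The cost is the wording of one paragraph. No participants are added and the analysis is unchanged; the stated sensitivity for the group contrasts becomes less favourable.

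### The 80% power statement for small-to-medium effects holds for a within-subject dose effect of d = .40, but not for the between-person effects it is applied to, where d = .40 has about 28% power

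*Combined protocol and SAP*

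**What the plan says.** Section 6, Power Analysis, states that the calculations "were performed assuming two-tailed hypothesis tests with alpha=.05". It then makes two claims for N=50. The first is 98% power for the dose effect on the QST measures (d > .58) and for the correlation between relief ratings and analgesia (r = .64). The second is that the same N will "provide 80% power to detect small-to-medium sized effects (d > .40; r > .37"; the full list of thresholds reads "d > .40; r > .37; R² > .14". The second claim covers effects that have no prior estimate, and its first example is the effect of chronic pain status on alcohol analgesia.

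The design has one within-subject factor (dose) and one between-subject factor (pain status). Section 6, Participants, sets 25 per group. The pain-status question is H3 in Section 5. H4 and H5 are tested by "Simultaneous multiple regression of alcohol analgesia expectancy and typical alcohol consumption" on the QST measures (Data Analysis Strategy, Aim 2), so they too concern differences between people. The paragraph says "Effect sizes are reported as Cohen's d, Pearson's r, or R2 (Cohen, 1988"), but prints no cut-offs for small, medium or large and does not say which test each threshold belongs to.

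**The concern.** The three thresholds stand under one size label and one power figure, as if they described the same sensitivity for any effect in the trial. The d threshold needs a paired contrast on all 50 people to reach 80%. The example offered is a comparison of two independent groups of 25, which is a much weaker test.

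This sentence is the only sensitivity statement that could cover H3, H4 and H5. Taken at face value, a non-significant pain-status interaction, or a non-significant slope for expectancy or drinking, could be read as evidence against small-to-medium effects. The Abstract says the study should supply effect-size data for future proposals, so such a reading could carry forward.

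**Working it through.** **Inputs.** N = 50, two-sided alpha .05, d = .40, r = .37, R² = .14 (Power Analysis); 25 per group (Participants); two predictors entered together (Data Analysis Strategy, Aim 2).

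**Step 1: reproduce the plan's 80%.**

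- Within-subject d = .40, all 50: noncentrality = .40 × √50 = 2.83, df = 49. Power **79.2%**.
- Correlation r = .37, t model: noncentrality = .37/√(1 − .1369) × √50 = 2.82, df = 48. Power **78.8%**. Fisher z: atanh(.37) × √47 = 2.66. Power **75.9%**.
- R² = .14, 1-df slope in the two-predictor model: λ = 50 × .14/.86 = 8.14, df = 1, 47. Power **79.8%**.
- The same R² as a 2-df overall test: df = 2, 47. Power **69.6%**.

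The 80% is therefore sound for the paired contrast and the 1-df slope, and nearly so for a single correlation.

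**Step 2: apply d = .40 to the plan's own example.** Pain status on analgesia compares the alcohol–placebo change between 25 and 25. With d on the SD of that change:

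- d = .40: noncentrality = .40 × √(25/2) = 1.41, df = 48. Power **28.3%**.
- d = .80: noncentrality 2.83, power 79.1%. d = .81: noncentrality 2.86, power **80.1%**.

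If d is scaled instead on the SD of a single session's score, an assumed within-person correlation ρ is needed. The change-score d is then .40/√(2(1 − ρ)):

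- ρ = 0: d = .283, power 16%
- ρ = .3: d = .338, power 22%
- ρ = .5: d = .400, power 28%
- ρ = .7: d = .516, power 43%

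**Step 3: put d and r on one scale for a between-person effect.** For two equal independent groups, r = d/√(d² + 4) and d = 2r/√(1 − r²):

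- d = .40 gives r = .40/√4.16 = **.196** (R² = .04).
- r = .37 gives d = .74/√.8631 = **.80**.

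For such effects the r threshold is about twice the d threshold.

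**Step 4: between-person sensitivity at N = 50.**

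- Minimum r for 80%: .375 (t model) or .387 (Fisher z).
- Minimum R² for 80%: .141 (1 df) or .170 (2 df).
- Power at r = .20: 28.5% (Fisher z) to 29.3% (t model).
- Power at r = .30: 56.4% (Fisher z) to 58.7% (t model).

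**Step 5: completers.** The plan recruits 60 and expects 10% dropout: 60 × .9 = 54. With an assumed 27 per group, d = .40 gives noncentrality .40 × √13.5 = 1.47, df = 52, power 30%. The conclusion is unchanged.

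**Step 6: the companion 98%.** Paired d = .58: noncentrality .58 × √50 = 4.10, power 98.0%. At r = .64, Fisher z gives atanh(.64) × √47 = 5.20, power above 99.9%. The 98% belongs to d = .58 alone.

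**The case against.** The strongest defence is that the three thresholds agree with each other once d is read as a within-subject effect. For a paired d the matching conversion is r = d/√(d² + 1), and d = .40 then gives r = .40/√1.16 = .371 and R² = .16/1.16 = .138, which are the plan's printed values. The thresholds are also in plain view, so a reader can see that r must exceed .37.

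Much of this stands. A reader might infer that the 80% was miscalculated, or that power at r = .37 or R² = .14 is really some 28–42%. The documents do not support either: power at those sizes is about 76–80% for a single correlation or 1-df slope, and the lower figures arise only at r of about .20 to .25, which the plan does not print. Nor do the documents show that d and r conflict on the within-subject reading. It is also tempting to call r = .37 larger than medium by conventional benchmarks, but the plan prints none, so the point cannot rest on them.

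The defence fails on the plan's own example. Pain status is a between-subject factor, so the paired reading that reconciles the three thresholds is not available for it. The sentence does not name H4 or H5, but it gives no other sensitivity for them, and they are between-person questions too.

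**Conclusion.** The thresholds are correctly computed for certain tests, but the sentence is wrong as applied. At N=50 the 80% holds for a within-subject dose effect of d about .40. For pain status with 25 per group, d = .40 has about 28% power, and 80% needs d of about .81. For expectancy and drinking, 80% needs r of about .37–.39 or a 1-df R² of about .14. For between-person effects the printed d and r differ about twofold on a common scale, so one size label cannot describe both.

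This rests on equal groups of 25, on d being expressed in SDs of the alcohol–placebo change (16–43% power on the single-session SD for an assumed ρ of 0 to .7), and on no covariate adjustment. It does not depend on any outside definition of small or medium. The r = .64 remark is minor: there the plan understates its power.

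**What to change.** Reword the power paragraph, with N unchanged:

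- State 80% power for a within-subject dose effect of d about .40.
- State separately that between-person effects (pain status, H3; expectancy and drinking, H4 and H5) reach 80% only at d about .81, r about .37–.39, or R² about .14 for a single slope. Say whether each R² refers to a 1-df or a 2-df test.
- Give power of about 28% at a between-group d of .40 or at r = .20, and about 56–59% at r = .30. Name the SD on which d is defined.
- Drop the small-to-medium label for between-person effects.
- State that a non-significant H3, H4 or H5 does not exclude effects below these sizes, and report each estimate with its 95% CI.
- Optionally, attach the 98% to d = .58 only and give r = .64 its own figure (above 99.9%).

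The cost is a few sentences and a less favourable sensitivity statement. No extra participants, visits or analyses are needed beyond reporting the intervals.
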